1.2. Schema

- Screening to dosing on Day 1 in Period 1: Maximum of 28 days for each cohort.
- Inpatient stay in each period: Day -1 to minimum of Day 3 (ie, 48 hours post-dose).
- In each period, 6 participants will be randomized to receive PF-07258669, and 2 participants will receive matching-placebo.
- Precautionary sentinel dosing will be used in each period of each cohort. Two participants (1 receiving PF-07258669 and 1 receiving placebo) within a period will be dosed initially before the remaining participants of that period are dosed. Safety and tolerability data through at least 24 hours post-dose for the sentinel participants will be reviewed prior to dosing the remaining participants of that period.
- The starting dose level in Period 1 of Cohort 1 is 0.1 mg. All other planned dose levels in other periods and cohorts may be adjusted pending emerging safety, tolerability, and PK data from previous periods and cohorts.
- On-site follow-up visit to occur on Day 8 ±2 days in Period 4 only, with an additional follow-up contact occurring 28-35 days after administration of the final dose of study intervention.

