Visit Identifier ^a	Screening		Period 1 to Period 4 ^b Follow-Up ET								ET/DC									
	Day -28	Day						Day	1						D	ay	Day	Visit:	Contact:	
	to Day -2	-1						-								2	3	Day	28-35	
Hours After Dose			0 ^d	0.17	0.5	1	1.5	2	4	6	8	10	12	16	24	36	48	8±2°	Days ^c	
Serum FSH ^r	Х																			
HBcAb, HBsAg, HBsAb, HCVAb, HIV testing	Х																			
Pfizer Prep B2 banked sample ^s			Х																	
Pfizer Prep D1.5 banked sample ^s			Х																	
PF-07258669 plasma pharmacokinetics			Х	Х	Х	Х	Х	Х	Х	Х	Х		Х	Х	Х	Х	Х			Х
CCI																				
Urine Samples for:																				
Urine drug test	Х	Х																		
Clinical safety laboratory tests ^q	Х	Х													Х		Х	Х		Х
Abbreviations: \rightarrow = ongoing/continuous event; AE = adverse event; BP = blood pressure; CRU = clinical research unit; DC = discontinuation; ECG = electrocardiogram;																				
ET = early termination; FSH = follicle stimulating hormone; HBcAb = hepatitis B core antibody; HBsAb = hepatitis B antibody; HBsAg = hepatitis B surface antigen;																				
HCVAb = hepatitis C antibody: HIV = human immunodeficiency virus: PR = pulse rate.																				

a. Day relative to start of study treatment (Day 1).

b. There will be a washout interval of ≥ 7 days between doses within an individual participant.

- c. Onsite follow-up visit to occur on Day 8 ±2 days in Period 4 only. Follow-up contact may occur via telephone contact and must occur 28-35 days after administration of the final dose of study intervention.
- d. Day 1 activities at time=0 hours are prior to the dose, except for study treatment administration.
- e. Participants may be confined to the CRU after completion of Day 3 activities at the discretion of the investigator or if safety, tolerability, or PK data dictate the need to prolong confinement in the CRU.
- f. Period 1 only. Review any changes from Screening.
- g. Contraception only required for male study participants and is recommended for partners of male study participants who are WOCBP.
- h. COVID-19 questionnaire includes check for suspected contact, risk zone, and COVID-19 related symptoms.
- i. Testing for active COVID-19 infection via testing for SARS-CoV-2 viral dosing (using PCR). To meet PCRU practice, testing for active COVID-19 infection will be performed at screening, admission, and follow-up visit.

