### 3.1.1. Adverse Events

All adverse events that start, or worsen in severity, on or after the date and time of the first dose but before the follow-up contact (28-35 days after last dose) will be flagged as Treatment-Emergent Adverse Events (TEAEs).

TEAEs will be assigned to the dose taken in the period they start in. Events that occur during a non-treatment period (for example, washout or follow-up) will be counted as treatment emergent and attributed to the most recent dose taken prior to the event.

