### **3.1.2. Clinical Safety Laboratory Tests**

Safety laboratory tests will be performed at the times specified in the Schedule of Activities in the protocol.

Baseline will be defined as the last non-missing pre-dose measurement for each period.

Any clinical laboratory abnormalities of potential clinical concern will be described. To determine if there are any clinically significant laboratory abnormalities, the haematological, clinical chemistry, urinalysis and other safety tests will be assessed against the criteria specified in the sponsor reporting standards. The assessment will take into account whether each participant's baseline test result is within or outside the laboratory reference range for the particular laboratory parameter.

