### **3.1.3. Vital Signs**

Supine blood pressure (BP) and pulse rate measurements will be taken at the times specified in the Schedule of Activities in the protocol. Orthostatic BP and pulse rate measurements will also be taken at additional times specified in the Schedule of Activities in the protocol. Note that some of the supine BP and pulse rate measurements are collected as part of the orthostatic assessment.

Baseline will be the Pre-Dose (0 hour) assessment on Day 1 of each period.

The following endpoints will be determined:

- Postural differences (supine - standing) for systolic and diastolic BP (at each orthostatic assessment timepoint)
- Postural differences (standing – supine) for pulse rate (at each orthostatic assessment timepoint)
- Change from baseline in supine, standing and postural differences for systolic and diastolic BP and for pulse rate
- The minimum and maximum post-dose supine and standing for systolic and diastolic BP and for pulse rate
- The maximum post-dose postural differences for systolic and diastolic BP and for pulse rate
- The maximum decrease and increase from baseline over all measurements taken post-dose for supine, standing and postural differences for systolic and diastolic BP and pulse rate.

The maximum increase from baseline will be calculated by selecting the maximum change from baseline over the respective period, except in the case where a participant does not show an increase. In such an instance, the minimum decrease should be taken. Similarly, the maximum decrease from baseline will be determined by selecting the minimum value of the changes from baseline. In cases where a participant does not show a decrease, the minimum increase should be taken.

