## **6. ANALYSES AND SUMMARIES**

### **6.1. Primary Endpoint(s)**

#### **6.1.1. Adverse Events**

Adverse events will be listed and summarized by treatment, in accordance with sponsor reporting standards using the safety population defined in Section 4.

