#### **6.1.2. Clinical Safety Laboratory Tests**

Laboratory data will be listed and summarized by treatment, in accordance with the sponsor reporting standards using the safety population defined in Section 4. Baseline is as defined in Section 3.1.2.

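### Does SAP 3.1.1 leave it open which dose an adverse event belongs to when it starts on Day -1 or before dosing on Day 1 of Periods 2-4?

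*SAP*

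**What the plan says.** SAP 3.1.1 counts an event as treatment-emergent if it starts or worsens from the first dose of the study until the follow-up contact. Two attribution sentences follow. The general one is "TEAEs will be assigned to the dose taken in the period they start in". The second concerns non-treatment periods, with washout and follow-up as examples; such events "will be counted as treatment emergent and attributed to the most recent dose taken prior to the event". SAP 6.1.1 then states "Adverse events will be listed and summarized by treatment, in accordance with sponsor reporting standards".

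On timing, Protocol 1.2 gives "Inpatient stay in each period: Day -1 to minimum of Day 3", and the table in Protocol 1.3 places Day -1 and the 0 h assessments under Periods 1 to 4. Footnote b of that table sets the washout as at least 7 "days between doses within an individual participant". The SAP also treats pre-dose time as part of a period, for example in 3.1.3: "Baseline will be the Pre-Dose (0 hour) assessment on Day 1 of each period".

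For laboratory data, SAP 3.1.2 says "Baseline will be defined as the last non-missing pre-dose measurement for each period", and 6.1.2 says "Laboratory data will be listed and summarized by treatment, in accordance with the sponsor reporting standards".

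**The concern.** Day -1 and the pre-dose hours of Day 1 in Periods 2-4 fit two descriptions. By the schema and the Schedule of Activities they lie in the coming period; by footnote b they lie in the washout after the previous dose. Taken literally, the general sentence assigns an event starting there to a dose not yet given, and the washout sentence assigns it to the dose already given. The SAP states neither the start of a period nor which sentence prevails.

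The window is not an idle one. In Periods 1-3 no visit or measurement is scheduled between 48 h and the next Day -1, apart from adverse event monitoring, which is continuous. Safety laboratory tests and a neurological examination fall on Day -1. ECG, orthostatic blood pressure, respiratory rate, temperature and another neurological examination fall at 0 h. A late change could first be found there, and Protocol 8.2.7 requires clinically relevant laboratory changes to be recorded as adverse events. If placebo followed an active dose, the literal general sentence would move the event from the active column to pooled placebo. That would bear on a primary endpoint.

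The laboratory sections raise a lesser question. They do not say which dose a value obtained after 48 h counts for.

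**Working it through.** **Inputs.** Eight participants per cohort, two planned cohorts and an optional third (Protocol 4.1, 9.2). Four periods, with 6 active and 2 placebo in each (Protocol 1.2). Each participant receives 3 active doses and 1 placebo dose (Protocol 4.2). Dosing is at 0800 h ± 2 h (Protocol 6.1.1). Washout is at least 7 days = 168 h.

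**Design check.** 3 × 8 = 24 participants, the stated maximum. Placebo doses per cohort: 8 × 1 = 8 by participant and 4 × 2 = 8 by period. Active doses: 8 × 3 = 24 and 4 × 6 = 24. The counts agree.

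**Transitions containing the window.** Each participant has 4 − 1 = 3, so a cohort has 8 × 3 = 24. With two participants on placebo in each of Periods 1 to 4:

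| Transition | Per cohort | 2 cohorts | 3 cohorts |
|---|---|---|---|
| Active to placebo | 2 × (0+1+1+1) = 6 | 12 | 18 |
| Placebo to active | 2 × (1+1+1+0) = 6 | 12 | 18 |
| Active to active | 24 − 6 − 6 = 12 | 24 | 36 |
| All | 24 | 48 | 72 |

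**Length of the window.** The admission time is not given. The longest case runs from 00:00 on Day -1 to dosing at 10:00 on Day 1: 24 + 10 = 34 h, and 34/168 = 20.2%. If the window opened only 12 h before dosing (an assumption), it would be 12/168 = 7.1%.

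**Effect of one reassigned participant.** At a dose level, 1/6 = 16.7 percentage points. In pooled placebo, 1/24 = 4.2 points with three cohorts or 1/16 = 6.3 points with two.

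**Reading the two sentences together.**

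1. After dosing in a period, the most recent dose is that period's dose, so both sentences give the same answer.
2. After discharge and before the next admission, the washout sentence applies and names the previous dose. The general sentence, read with the period running on, names the same dose.
3. On Day -1 and before dosing on Day 1 of Periods 2-4, the time is still between doses and so is washout under footnote b. The specific sentence applies and names the previous dose. The general sentence presupposes a dose that has been taken, and in that period none has.
4. On Day -1 and before dosing in Period 1, the event precedes the first dose of the study, so attribution arises only if it later worsens after a dose.

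Every case resolves to the most recent dose actually given.

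**Laboratory values.** The Day 8 ± 2 visit occurs in Period 4 only, after the last dose. An early-termination visit ends dosing for that participant (Protocol 7.2). Neither has a later dose competing for the value. The Day -1 sample is the scheduled pre-dose sample and so serves as the period's baseline. What remains is unscheduled washout samples, and whether a Day -1 value also counts as a late value for the previous dose. Both are left to the sponsor's reporting standards. A clinically relevant change is recorded as an adverse event and follows the attribution above.

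**The case for a change.** The strongest case for a change is that the specific-over-general reading makes the first sentence redundant. If washout means all time between doses, the second sentence covers everything up to the last dose. To give the first sentence work to do, washout must be narrower, meaning time outside the periods. Day -1 then belongs to the coming period, and the literal answer is the dose not yet given. Half of the transitions (36 of 72) switch between active and placebo, and in the active-to-placebo direction (18 of 72) a drug event would be hidden in the placebo column. One sentence would remove the doubt.

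Part of this stands: the period start is undefined, no precedence is stated, and the counts are right. The redundancy argument carries less weight. A general rule followed by a clarification for time away from the unit is ordinary drafting, and overlap with the same answer does no harm. The narrower reading would attribute an event to a treatment the participant had not received, which a competent analyst would reject.

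The gain from rewriting is also small. A replacement sentence would largely repeat the existing washout sentence. If keyed to onset alone it would lose something, because events that began before the first dose and worsened later are treatment-emergent but have no dose before their onset.

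SAP Figure 1 and the sponsor's reporting standards cannot be seen in the public documents, so it cannot be established that the boundary is undefined everywhere.

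**Conclusion.** No change is needed. The overlap in the wording is real, but following both sentences leads to attribution to the most recent dose given. The missing period boundary is a gap that analysts fill sensibly.

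The window is at most about 34 h before the next dose, at 72 transitions (48 with two cohorts). Only events whose onset or worsening is dated inside it are touched; a symptom reported on Day -1 that began earlier in the washout is not. How many events that would be cannot be worked out from the documents. The shift of 16.7 points per participant reflects groups of six and says nothing about how likely a reassignment is.

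The consequences are limited as well. SAP 5.1 has no hypothesis tests or decision rules, and the SAP analyses follow database lock. Dose escalation rests on review by the investigator and study team during the trial (Protocol 6.6, 6.6.1 and 9.5), and individual events are listed. The laboratory point is missing detail deferred to sponsor standards, with no competing dose at the Period 4 follow-up or early-termination visits.

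This conclusion assumes that the washout in SAP 3.1.1 has the meaning given in Protocol 1.3, footnote b, and that unseen sponsor standards do not direct events to a dose not yet taken.

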## 2.2. Study Design

*This study is a randomized, investigator- and participant-blind, sponsor-open, placebo-controlled, first-in-human, single ascending oral dose study of PF-07258669 administered to healthy adult participants. Up to approximately 24 healthy adult participants (up to 3 cohorts of approximately 8 participants each) will be enrolled in this study. Each participant is planned to undergo 4 treatment periods receiving 3 doses of PF-07258669 and 1 dose of placebo.*

*Precautionary sentinel dosing will be used in each period of each cohort. Two participants (1 receiving PF-07258669 and 1 receiving placebo) within a period will be dosed initially before the remaining participants of that period are dosed. Safety and tolerability data through at least 24 hours post-dose for the sentinel participants will be reviewed prior to dosing the remaining participants of that period.*

[figure not shown]
*Dose levels will be escalated to bracket the expected clinical dose range, but projected exposures will not exceed the pre-defined human exposure limits. The optional third cohort will only be used if the objectives of the study are not fulfilled in Cohort 1 and Cohort 2. The total duration of participation from the screening visit to the telephone follow-up contact will be approximately 14 weeks.*

A starting dose of 0.1 mg of PF-07258669 is planned.

*If a participant drops out before completing all study periods within a cohort, or withdraws for reasons unrelated to the safety of the study intervention, the participant may be replaced at the discretion of the investigator and sponsor. The replacement participant(s) may or may not be required to complete all periods of the cohort in which they are participating at the discretion of the investigator and sponsor.*

Figure 1 shows the study design.

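### AE incidence by treatment is not comparable across doses, because SAP 3.1.1 sets no common post-dose window and a cohort's last dose collects events for longer than its earlier doses

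*SAP*

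**What the plan says.** SAP 3.1.1 flags treatment-emergent events from the first dose onward "but before the follow-up contact (28-35 days after last dose"). An event is assigned to the dose of the period in which it starts. Events in washout or follow-up "will be counted as treatment emergent and attributed to the most recent dose taken prior to the event". SAP 6.1.1 states the only planned presentation: "Adverse events will be listed and summarized by treatment, in accordance with sponsor reporting standards". SAP 5.2.2 gives counts and percentages for categorical data. Neither section states a common post-dose window, a time-at-risk denominator or a sensitivity table.

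The timing comes from elsewhere:

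- Protocol 1.3, footnote b: "There will be a washout interval of ≥ 7 days between doses within an individual participant".
- SAP 2.2: "The total duration of participation from the screening visit to the telephone follow-up contact will be approximately 14 weeks".
- Protocol 1.2, on screening: "Screening to dosing on Day 1 in Period 1: Maximum of 28 days for each cohort".
- Protocol 1.2, on allocation: "In each period, 6 participants will be randomized to receive PF-07258669, and 2 participants will receive matching-placebo".
- Protocol 1.2, on the visit after the last dose: "On-site follow-up visit to occur on Day 8 ±2 days in Period 4 only".

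**The concern.** Adverse events are a primary endpoint. Under the rule, a dose's time at risk depends on its position in the sequence. A Period 1, 2 or 3 dose stops collecting events when the next dose is given, whereas the Period 4 dose collects them until the follow-up contact. With no drug effect at all, the last dose is then expected to show a higher percentage of participants with events, and in an ascending design that can look like a dose response. Period 4 need not hold the highest dose, since Protocol 6.6 allows levels to be decreased or repeated, so the ordering of doses can be distorted in other ways too.

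Two comparisons are unaffected. Period 4 active and Period 4 placebo share the same window, though only 2 placebo participants per cohort contribute. All active doses against all placebo doses is also balanced. The affected comparisons are dose against dose, and a single dose against placebo pooled over periods. Pooled placebo is stated for the safety plots (for example SAP 6.1.3); for the AE table it is an assumption.

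**Working it through.** **Design check.** Per participant, 4 × 6/8 = 3 active doses and 4 × 2/8 = 1 placebo dose, as the plan states. The Period 4 share per cohort is 6/24 = 25% of active doses and 2/8 = 25% of placebo doses, so the all-active versus all-placebo comparison is balanced.

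**Attribution windows.** Take 14 weeks = 98 days, screening S days, final follow-up F = 28 or 35 days, and three dosing intervals. The mean interval is w = (98 − S − F)/3.

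- S = 28: w = 14.0 (F = 28) or 11.67 (F = 35); F/w = 2.0 or 3.0.
- S = 2: w = 22.67 (F = 28) or 20.33 (F = 35); F/w = 1.24 or 1.72.
- Minimum washout, w = 7: F/w = 4 or 5. Total time would then be between 2 + 21 + 28 = 51 days and 28 + 21 + 35 = 84 days (7-12 weeks). That does not fit 14 weeks, so this is a floor case only.

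**Effect on incidence.** The documents give no AE rate, so the hazards are assumptions, with no drug effect. P(t) = 1 − exp(−H(t)). Pooled placebo = 0.75 P(w) + 0.25 P(F). Excess = 6 × [P(F) − P(w)].

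- Front-loaded: 5%/day for 2 days, then 0.5%/day, so H(t) = 0.10 + 0.005(t − 2). This is the lead case, because monitoring is intensive to 48 hours and sparse afterwards.
- Low late hazard: H(t) = 0.10 + 0.001(t − 2).
- Constant: H(t) = 0.01t.

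| Case | w, F (days) | Earlier dose | Last dose | Pooled placebo | Ratio to earlier | Ratio to placebo | Excess of 6 |
|---|---|---|---|---|---|---|---|
| Front-loaded | 14, 28 | 14.8% | 20.5% | 16.2% | 1.39 | 1.27 | 0.35 |
| Front-loaded | 11.67, 35 | 13.8% | 23.3% | 16.2% | 1.69 | 1.44 | 0.57 |
| Front-loaded | 22.67, 28 | 18.4% | 20.5% | 18.9% | 1.12 | 1.09 | 0.13 |
| Front-loaded | 20.33, 35 | 17.4% | 23.3% | 18.9% | 1.33 | 1.23 | 0.35 |
| Low late | 14, 28 | 10.6% | 11.8% | 10.9% | 1.12 | 1.09 | 0.07 |
| Low late | 11.67, 35 | 10.4% | 12.5% | 10.9% | 1.20 | 1.14 | 0.12 |
| Low late | 22.67, 28 | 11.4% | 11.8% | 11.5% | 1.04 | 1.03 | 0.03 |
| Low late | 20.33, 35 | 11.2% | 12.5% | 11.5% | 1.12 | 1.08 | 0.08 |
| Constant | 14, 28 | 13.1% | 24.4% | 15.9% | 1.87 | 1.54 | 0.68 |
| Constant | 11.67, 35 | 11.0% | 29.5% | 15.6% | 2.68 | 1.89 | 1.11 |
| Constant | 22.67, 28 | 20.3% | 24.4% | 21.3% | 1.20 | 1.15 | 0.25 |
| Constant | 20.33, 35 | 18.4% | 29.5% | 21.2% | 1.61 | 1.39 | 0.67 |

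**Chance of a spurious top ranking.** Front-loaded case, independent binomial counts with n = 6: the probability that one level is strictly highest is the sum over k of P(X = k) × the product of P(other count < k).

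- Four levels in one cohort: 0.236 and 0.303 at 14 and 11.67 days; 0.180 and 0.236 at 22.67 and 20.33 days. That is 18-30%, against 14-15% with equal windows.
- The same comparison simulated with the same eight participants in all four periods (shared gamma frailty, variance 1 or 2): about 20-28% at 11.67-14 days, against 13-14%.
- Eight levels in two cohorts, two of them with the long window: 11-15% for a given long-window level at 11.67-14 days, against 6.5%.

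**The case against.** Several points on the other side stand.

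- A reader might infer that attribution never ends. It does: the treatment-emergent flag stops at the follow-up contact. What is missing is a window common to all doses.
- A reader might take a four- to fivefold difference in window as typical. It arises only at the 7-day minimum washout, which the stated 14 weeks contradicts.
- A reader might fear for dose escalation. Protocol 6.6.1 bases escalation on review of safety data to at least 48 hours, and the sponsor may review unblinded data throughout (Protocol 9.5). Neither depends on the final AE table. SAP 5.1 rules out hypothesis tests and statistical decision rules.
- Protocol 10.3.3 requires the investigator, who is blinded, to judge the causality of every event, including its timing relative to dosing. That is a real safeguard against reading late background events as drug effects. However, the SAP text does not promise a table of related events, so the safeguard may not reach the incidence summary.
- SAP 6.1.1 defers to sponsor reporting standards that are not available here. They may include onset-day or related-event displays. The study-specific rule in SAP 3.1.1 contains no window.
- Dose is confounded with period within a cohort by design, so no window makes dose-to-dose comparison clean. That limits what the fix achieves, but it is no reason to add a second, avoidable imbalance.

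**Conclusion.** The point holds as one of comparability, and it is minor. Within a cohort, the last dose has about 1.2-3 times the attribution window of the earlier doses if 14 weeks holds. Its crude AE incidence is raised relative to those doses, and relative to pooled placebo if pooling applies, whenever the late background rate is above zero. Confidence in the direction is high.

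Confidence in the size is medium, because every hazard is assumed. The excess is 0.13-0.57 of 6 participants in the front-loaded case, and runs from 0.03 to about 1.1 over all cases at intervals consistent with 14 weeks. The ranking probabilities further assume independent counts and distinct dose levels. The window calculation assumes participants who complete all four periods.

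The documents do not support the stronger inference that the trial's safety conclusions or escalation decisions are biased. What is affected is how the final descriptive AE tables are read across doses.

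**What to change.** Keep the attribution rule and the full-window AE table. Add the following to SAP 6.1.1:

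1. A by-treatment AE incidence table on one window for every dose and for placebo: from dosing to the earlier of the next dose or 7 days post-dose.
2. A separate listing of later events, still attributed to the most recent dose, with onset day and investigator causality.
3. A flag for events first detected at the on-site follow-up visit that exists only in Period 4.
4. A sentence stating that dose-to-dose and pooled-placebo comparisons of AE incidence use the common-window table.

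The cost is one table, one listing, one flag and a few lines of text, using onset times that SAP 3.1.1 already needs. It requires no new visits, data or participants, and no late event leaves the existing summaries.

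One limit remains. Day 8 ±2 is 5-9 days after dosing, so the Period 4 visit can fall inside the 7-day window and ascertainment is not fully equalised. The flag shows this difference but does not remove it.
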